### 7.3 General information regarding TAVI procedure

TAVI procedure will be performed in accordance with current guidelines and institutional standards. TAVI procedure will be performed by the study TAVI operators. The decision regarding site access management, valve type and size will be left to study TAVI operators. The monitoring after the TAVI procedure and the subsequent mobilization and management of the patient will be in accordance with current guidelines and institutional standards.

### 7.4 Data collection and Case Report Form

[figure not shown]
The study investigators will be monitored for consecutive recruitment of patients. A registry of excluded patients will be updated monthly and if selection bias is noticed, it would lead to the exclusion of the center from the investigation. Data will be collected in electronic case report forms (eCRF). The eCRF will be web-based and all investigators will receive specific credentials for the access. The eCRF will also include the web-based tool for randomization. The quality of the data included in the eCRF will be reviewed by the Academic Research Organization (ARO) of the University Hospital of Ferrara. The eCRF will contain a dedicated tool to report adverse events.

### 7.5 Follow-up

After hospital discharge, routine clinic follow-up will occur at 1, 6, 12 months and then yearly thereafter up to 3 years. At each visit, clinical outcomes, compliance with medical therapy, and quality of life (EQ-5D) will be assessed.

[figure not shown]
## 7.6 Study collection of adverse events

All adverse events must be reported by the study investigators. The Academic Research Organization will collect the source document of all adverse events. Adverse events will be adjudicated by the Clinical Event Committee (CEC). As reported below, the CEC will transfer to DSMB the adverse events.

## 7.7 Adjudication of clinical events

A committee consisting of clinicians who are blinded to treatment allocation will adjudicate all adverse events. The functioning rules and the membership of the Adjudication Committee are detailed in the Adjudication Committee Charter before the start of the trial. The adjudication results will be binding for the final analysis.

## 7.8 Role of the Data Safety Monitoring Board (DSMB)

The DSMB is responsible for the following items:

- Approval of the participating centers
- Approval of the study TAVI operators
- Analysis of the rate of adverse events in the study arms
- Monitoring of study conduction and of the distribution of valve type and valve brand between study arms

The DSMB is responsible for immediately stopping the trial if the rate of adverse events would be higher than expected. DSMB will strictly monitor the rate of periprocedural complications that require emergent cardiac surgery in the experimental arm and the rate of adverse events while on the TAVI waiting list in the control arm.

Based on previous studies, we assume that the rate of periprocedural complications requiring emergent cardiac surgery should not exceed 2% (minimum number of patients for the analysis n=75), whereas the rate of adverse events during the waiting time for TAVI in the control arm should not exceed 15% (minimum number of patients for the analysis n=100). Anyway, the DSMB:

- will be immediately informed after each periprocedural complication requiring emergent cardiac surgery
- will generate a report each 4 months illustrating the trend of adverse events (in line with or not with the expectations)
- will communicate each 4 months to the Steering Committee if the study can continue or not.

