Clinical Event Adjudication Committee	A blinded Clinical Event Adjudication Committee will adjudicate adverse events.
Data and Safety Monitoring Board	An independent Data and Safety Monitoring Board will advise the Steering Committee on the safety aspects and overall progress of the study.
Statistical Considerations	The estimated rate of the primary endpoint is around 30%, considering the characteristics of the study population and the inclusion of adverse events before TAVI [1-29]. Overall, 560 (187 control arm and 373 experimental arm) patients are required to exclude a difference in favor of the control group of more than 10% ( $\alpha=5\%$ and $\beta=20\%$ ). Considering a 1% attrition rate final sample size is inflated to 566 patients.

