**Seventeen patients (10%) died while waiting for a complete assessment** [18]. A group from Almada, Portugal, reported in the 2020 ESC annual meeting on 120 consecutive AS patients (54% male, mean age  $75 \pm 9$  years) referred between 2014 and 2018 to a single center. During the waiting period, there were 13 (11%) patients who were hospitalized due to heart failure and 7 (6%) patients who died. The median time between referral and the occurrence of the primary endpoint was 3 months [42]. In Israel,, data on mortality of patients with AS diagnosed in 9 non-TAVI centers and referred to a TAVI center found that during a six-month period in 2019 there were 203 patients patients referred with a mortality rate of 4.9% (10/203) during the waiting period [19]. **Data from Ontario (Canada) showed that during the initial period of development of TAVI therapy, patients with TAVI showed mortality rates of 10% to 14% while in the waiting period** [20]. **In Ontario from 2010 to 2016, the cumulative probability of TAVI wait list mortality was 4.3% in a predominantly inoperable and high-risk population** [21]. From recent reports, the cumulative probability of wait-list mortality and heart failure hospitalization at 80 days in Canada was 2% and 12%, respectively, with a relatively constant increase in events with increased waiting times. From a cohort consisting of 22,876 referrals for aortic valve replacement, with (n = 8098) TAVI and (n = 14,778) SAVR referrals, the mean and median waiting times for the overall AVR cohort were 87 and 59 days, respectively. The TAVI sub cohort had longer waiting times (median 84 days) compared with the SAVR sub cohort (median 50 days). **Year over year, there was a statistically significant increase in wait-times ( $p < 0.001$ ) for TAVI. The waiting time mortality was 5.2% for TAVI, while the cumulative probability of hospitalization for heart failure was 7.7%** [21]. Current waiting time for TAVI in Italy ranges from 2 to 6 months, with a strong variability based on regional healthcare system organization. In the Emilia-Romagna region, the median wait time is m 6 months in 52% of patients scheduled for TAVI (Direzione Generale Cura della Persona, Salute e Welfare, Regione Emilia-Romagna).

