### 3 HYPOTHESIS

Based on this background, we hypothesize that in patients with severe symptomatic aortic stenosis (inoperable or at high surgical risk) TAVI procedure can be performed by experienced operators in centers without on-site cardiac surgery (CS) with a similar 1-year outcome compared to centers with on-site cardiac surgery. Indeed:

- Bleeding, access site-related complications, and pacemaker implantation are the most common complications of TAVI and their treatment does not require on-site cardiac surgery
- Complications needing emergent cardiac surgery are very rare (<1%) and, despite the surgical intervention, the mortality in this population remains very high (more than 50% at 30 days, near 80% at 1 year)
- A median waiting time for TAVI around 3 months before TAVI is associated with a risk of mortality and hospitalization for heart failure around 4% and 15%, respectively. There is a relatively constant increase in the probability of death or of hospitalization with increasing waiting times, with no threshold below which events rates flat.
- To allow the treatment of inoperable or high surgical risk patients in centers without on-site cardiac surgery, can significantly reduce the waiting time for TAVI (also in the center with on-site CS) and then the fatal adverse events that occur between the indication for TAVI and the TAVI itself.

Therefore, we assume that an indication shared by an experienced Heart Team and a procedure meticulously planned and performed by experienced operators are the most effective strategies to minimize periprocedural complications, independently of the presence or absence of on-site CS. This hypothesis is indirectly confirmed by preliminary analyses from centers performing TAVI without on-site CS. Therefore, the aim of the TRACS trial is to investigate if a TAVI pathway based on experienced operators who perform the procedure in the center without on-site cardiac surgery is non inferior compared to the one with the same team who perform the procedure in the center with on-site cardiac surgery in terms of outcomes..

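### The 15% waiting-list limit given to the DSMB in Section 7.8 equals or lies below the rate that Section 3 expects for a three-month wait

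*Protocol*

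**What the plan says.** Section 7.8 gives the DSMB a stopping duty: "The DSMB is responsible for immediately stopping the trial if the rate of adverse events would be higher than expected". The next paragraph supplies the only numbers attached to that expectation. For the experimental arm, "the rate of periprocedural complications requiring emergent cardiac surgery should not exceed 2% (minimum number of patients for the analysis n=75". For the waiting list, "the rate of adverse events during the waiting time for TAVI in the control arm should not exceed 15" per cent, judged from at least 100 patients. The adverse events that count towards the 15% are not named.

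Section 7.8 also has the DSMB informed after every complication that requires emergent surgery, and has it report, and tell the Steering Committee whether the study can continue, every 4 months.

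Section 3 states that a median wait of around 3 months "is associated with a risk of mortality and hospitalization for heart failure around 4% and 15%, respectively". It adds that events rise fairly constantly as the wait lengthens. Section 2.5 puts current Italian waits at 2 to 6 months and cites several series, among them one in which "the cumulative probability of wait-list mortality and heart failure hospitalization at 80 days in Canada was 2% and 12%, respectively".

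The Synopsis describes the DSMB differently: "An independent Data and Safety Monitoring Board will advise the Steering Committee on the safety aspects and overall progress of the study".

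**The concern.** A monitoring limit should be unlikely to be crossed when the trial behaves as its designers expect. Here the waiting-list limit is no higher than the expectation in Section 3, before any event other than death or heart-failure admission is counted.

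If the limit were applied as a crude rate, the control arm could trigger the stopping duty because usual care performs as the hypothesis says it will. The non-inferiority question might then go unanswered. If instead the DSMB learned to disregard the limit, the protocol would have no working safety rule on the waiting list.

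**Working it through.** The protocol gives no derivation for either limit, so there is no figure to reproduce. The check asks how often each limit is crossed at rates the protocol itself states.

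**1. Rate implied by Section 3.** Inputs: death 4%, heart-failure admission 15%.
- Full overlap: max(4, 15) = 15%.
- No overlap: 4 + 15 = 19%.
- Independence (an assumption): 1 − 0.96 × 0.85 = 18.4%.

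The 15% to 19% bounds need no assumption about overlap. Other adverse events can only raise the rate.

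**2. Crossing at 100 controls.** 15/100 does not exceed 15%; 16/100 does. With X binomial(100, p), P(X ≥ 16) is:

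| True rate p | Source | P(cross) |
|---|---|---|
| 15% | Section 3, full overlap | 0.43 |
| 18.4% | Section 3, independence | 0.77 |
| 19% | Section 3, no overlap | 0.81 |
| 12% | Section 2.5, 2% and 12%, full overlap | 0.14 |
| 12.9% | Section 2.5, 5.2% and 7.7%, no overlap | 0.21 |
| 14% | Section 2.5, 2% and 12%, no overlap | 0.32 |
| 17% | Section 2.5, 6% and 11%, no overlap | 0.65 |

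Full overlap of 5.2% and 7.7% would give 7.7%, where crossing is below 1%.

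**3. Repeated looks, waiting list.** Assume 187 controls accrue evenly over 24 months, about 187/6 = 31 per 4-month period. The 4-monthly looks with at least 100 controls then fall near 125, 156 and 187, where the limit is crossed at 19, 24 and 29 patients.
- Looks at 125, 156 and 187: P(ever crossing) is 0.60 at 15% and 0.95 at 19%.
- First look exactly at 100, then 4-monthly (132, 163, 187): 0.63 at 15% and 0.95 at 19%.

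**4. Surgery limit.** Expected rates are 0.76% (the transfemoral registry in Section 2.4) and 1% (10 per 1000 in Section 2.6). At n = 75, 1/75 = 1.3% and 2/75 = 2.7%, so two events breach 2%. P(X ≥ 2) = 1 − (1 − p)^75 − 75p(1 − p)^74:
- p = 0.76%: 1 − 0.5643 − 0.3241 = 0.11.
- p = 1%: 1 − 0.4706 − 0.3565 = 0.17.

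Under even accrual of 373 patients (about 62 per 4 months), the first eligible 4-monthly look falls near 124, where three events are needed (2/124 = 1.6%; 3/124 = 2.4%). Over 4-monthly looks from 124 to 373 the chance of ever crossing is 0.10 at 0.76% and 0.20 at 1%. Adding a look at 75 raises these to 0.16 and 0.26.

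**The case against.** A reader might infer more than the protocol supports, in four ways.

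*Both limits conflict with the expected rates.* They do not. The surgery limit of 2% is at least twice the expected rate, which Section 3 puts below 1%. What remains is a coarse rule at small numbers. Its repeated-look figures depend on a schedule the protocol does not fix.

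*The 15% limit contradicts the rate used for planning.* The only rate in the sample-size calculation (Section 9.1) is 30% at one year. The benchmark here is the approximate expectation in Section 3. Section 7.8 says its limits rest on previous studies, and some of those in Section 2.5 combine to below 15%. On those figures crossing at 100 controls is clearly the less likely outcome.

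*The trial will probably stop if its assumptions hold.* At exactly 15%, a single look at 100 controls crosses with probability 43%, below one half. Crossing becomes more likely than not only at higher rates within the Section 3 range or over repeated looks.

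*Crossing ends the trial automatically.* Section 7.8 introduces the numbers as assumptions, in a paragraph separate from the stopping sentence, and goes on to describe trend reports and communication to the Steering Committee. That last step fits the advisory role in the Synopsis. Formal boundaries may also sit in a DSMB charter or analysis plan, so their absence from the protocol is not the complaint.

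These objections narrow the point but leave its core. The stopping sentence turns on events exceeding expectation, these are the only numbers given for that expectation, and the waiting-list number does not agree with Section 3. If review rather than stopping is meant, the text does not say so.

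**Conclusion.** The point holds for the waiting-list limit. Section 3 implies 15% to 19% for death or heart-failure admission over a wait of about 3 months; Section 7.8 sets 15% for undefined adverse events. A control arm behaving as Section 3 expects crosses the crude limit at 100 patients with probability 43% to 81%, and over looks up to 187 controls with probability about 60% to 63% (true rate 15%) or 95% (19%). On the 12% to 14% reading of Section 2.5, the figure at 100 patients is 14% to 32%.

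These results assume a crude proportion of patients with an event, independent patients and completed waits of about 3 months. The repeated-look figures also assume even accrual over 24 months. Longer waits, or a wider definition of adverse event, would push the probabilities up.

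The surgery limit is a secondary point: consistent with the expected rate, but breached by two events in 75, with probability 11% to 17% at 0.76% to 1%. The mismatch between an advisory and a stopping DSMB is a matter of wording that should be settled at the same time.

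**What to change.** - Reconcile Sections 3 and 7.8, so that the waiting-list expectation and the waiting-list limit rest on the same events, the same length of wait and a stated source. The choice of limit belongs to the sponsor and the DSMB.
- Name the waiting-list adverse events that count, and say whether the rate is of patients or of events.
- State whether crossing a crude limit triggers an unscheduled DSMB review or stops the trial.
- Base any recommendation to stop on a pre-stated criterion that allows for sampling error and for the planned looks, and tabulate its false-trigger rates at the expected rates, for both limits.
- Use one description of the DSMB's role, advising or stopping, in the Synopsis and Section 7.8.

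The cost is a rewording of Section 7.8, a matching DSMB charter and a short table of operating characteristics. The drawback is that a criterion allowing for sampling error reacts more slowly at small numbers. For surgical complications, the existing immediate notification of each case offsets this. Section 7.8 gives no such immediate notice for waiting-list events, so the sponsor should consider whether the 4-monthly report is enough.

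### Section 7.8 sets a 15% maximum for control-arm waiting-list events, at or below the rate Section 3 predicts for usual care, and leaves unclear whether a breach means review or an immediate stop

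*Protocol*

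**What the plan says.** Protocol Section 7.8 contains three statements that bear on this point.

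- On consequence: "The DSMB is responsible for immediately stopping the trial if the rate of adverse events would be higher than expected".
- On level: based on previous studies, and introduced as an assumption, "the rate of adverse events during the waiting time for TAVI in the control arm should not exceed 15" per cent, with at least 100 patients needed for the analysis. The same sentence gives 2% (at least 75 patients) for complications requiring emergent cardiac surgery.
- On process: the board reports every 4 months on whether events follow expectations, and "will communicate each 4 months to the Steering Committee if the study can continue or not".

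The synopsis describes the board's role differently: it "will advise the Steering Committee on the safety aspects and overall progress of the study".

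Section 3 gives the expected rates under usual care. A median wait of about 3 months carries a "risk of mortality and hospitalization for heart failure around 4% and 15%, respectively". It adds: "There is a relatively constant increase in the probability of death or of hospitalization with increasing waiting times". Section 2.5 gives Italian waits of 2 to 6 months, and Section 7.2 leaves the control patient's wait to the referring center's list.

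Section 8.12 says that heart-failure hospitalization and emergent balloon valvuloplasty between randomization and TAVI will be closely monitored. It mentions neither death nor the 15% figure.

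**The concern.** The trial's rationale is that waiting for a slot at the surgical center costs lives and admissions. A control arm with that cost is what the hypothesis predicts. Section 7.8 nevertheless sets the control-arm waiting-list maximum at the size of the heart-failure component alone in Section 3, and places it directly after a sentence that calls for an immediate stop when events exceed expectation.

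If the board follows that sentence, the trial could end because usual care performed as hypothesised. Stopping would not shorten the wait of the control patients concerned. It would leave the non-inferiority question with part of the sample, and a control-arm rate alone does not show whether the experimental pathway is worse.

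If 15% is only a benchmark, it is still hard to apply. It is tied to no length of wait, and 7.8 does not say which adverse events count towards it.

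**Working it through.** **Origin of the 15%.** The protocol gives no derivation beyond a reference to previous studies, so there is no formula to reproduce. The figure can only be compared with the protocol's other numbers.

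**Expected rate of either event.** The proportion with death or heart-failure admission runs from the larger component (full overlap) to the sum (no overlap).

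| Source | Death | HF admission | Either event |
|---|---|---|---|
| Section 3, about 3 months | 4% | 15% | 15% to 19% |
| Section 2.5, Canada, 80 days | 2% | 12% | 12% to 14% |
| Section 2.5, Canada, TAVI referrals | 5.2% | 7.7% | 7.7% to 12.9% |
| Section 2.5, Portugal, 120 patients | 7 (6%) | 13 (11%) | 10.8% to 16.7% |

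If the two Section 3 events were independent, the figure would be 1 − 0.96 × 0.85 = 18.4%. The Canadian rows rest on "the cumulative probability of wait-list mortality and heart failure hospitalization at 80 days in Canada was 2% and 12%, respectively" and "The waiting time mortality was 5.2% for TAVI, while the cumulative probability of hospitalization for heart failure was 7.7" per cent.

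**Chance of observing more than 15% at 100 patients.** This needs 16 or more events: 1 − BinomCDF(15; 100, p).

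| True rate p | Probability |
|---|---|
| 12% | 0.141 |
| 12.9% | 0.215 |
| 14% | 0.323 |
| 15% | 0.432 |
| 16.7% | 0.616 |
| 19% | 0.812 |

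Over Section 3's own range of 15% to 19%, the chance is 43% to 81%.

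**Repeated looks.** The board reports every 4 months, so more than one look is likely, but the protocol does not fix accrual or the denominator.

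- Two looks at months 16 and 20, assuming 189 controls accrued evenly over 24 months, a 3-month wait and all enrolled controls in the denominator: 42% at a true 15% and 85% at 19%.
- Four looks at 100, 125, 150 and 187 controls with complete waits: about 63% and 95%.

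The spread comes from the assumptions. The single look is the cleaner figure.

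**Dependence on the wait.** With a constant rate (an assumption consistent with Section 3), the risk at t months is 1 − (1 − r)^(t/3), where r is the 3-month risk.

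- r = 15%: 10.3% at 2 months, 27.8% at 6 months.
- r = 19%: 13.1% at 2 months, 34.4% at 6 months.

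The same underlying event rate would therefore fall under 15% with a 2-month list and well over it with a 6-month list.

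**What an early stop would cost.** Power = Φ(0.10 / √(0.21 × (1/n + 1/(2n))) − 1.645), with n controls, 30% in both arms, one-sided 5% and follow-up completed.

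- n = 187 (planned): 0.79, against the stated 80%.
- n = 158 (month 20): 0.72.
- n = 126 (month 16): 0.64.

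The last two apply only if 15% is used as a stopping limit and recruitment ends at that look.

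**The case against.** A reader might infer that the protocol requires the trial to stop once the control arm passes 15%. The documents do not support that. No sentence links the figure to the stop. It is worded as an assumption, followed by a 4-monthly statement on whether the study can continue, and the synopsis makes the board advisory. Read together, these favour a reference value for judgement. This objection stands, and it confines the breach and power figures to the strict reading. It does not remove the stop sentence, which is followed directly by the rates that define expectation.

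A reader might also infer that 15% is below everything the protocol cites. It is not. On heart-failure admission alone it equals Section 3 and exceeds all three cohort rates in Section 2.5 (12%, 7.7%, 11%). Counting death as well, with no overlap, two of the three cohorts stay below it. Section 3 also hopes for shorter waits at the surgical center, which would lower the rate. What remains is that the level has little or no room above the protocol's own expectation: even at a true 14%, one look breaches it about a third of the time.

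Finally, it would be wrong to say that the protocol names no waiting-period events or that the board sees only controls. Section 8.12 names two closely monitored events, and 7.8 lists analysis of adverse events in the study arms among the board's duties. Neither says which events the 15% counts, or over what wait.

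A DSMB charter could add detail, but the 15%, the minimum of 100 and the stop sentence are fixed in this protocol.

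**Conclusion.** The point holds in a limited form. Section 7.8 sets a control-arm waiting-list maximum that Section 3's expectation meets or exceeds by up to 4 percentage points, and it does not settle what exceeding that maximum triggers. On the strict reading, usual care performing as Section 3 predicts would breach the figure at a single look with probability 43% to 81%. At the lower rates of 12% to 14% from the 80-day Canadian cohort, the probability is 14% to 32%.

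These figures assume that death or heart-failure admission is what counts, that overlap lies between none and complete, and that 100 controls have completed their wait. Counting other adverse events or longer waits would raise them; shorter waits would lower them. Monitoring waiting-list events is sound. The fault lies in the level and its unclear consequence. It should be corrected before the figure is used, with medium confidence, because the harm depends on how the board reads the text.

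**What to change.** Amend Section 7.8 as follows.

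- State that a control-arm waiting-list rate above 15% prompts DSMB review, read against the experimental arm's events from randomization, and is not by itself a reason to stop.
- Tie the 15% to named events: death or heart-failure hospitalization between randomization and TAVI, with the emergent valvuloplasty already named in 8.12.
- Tie it to a stated wait, for example 3 months. With a constant rate this is −ln(0.85)/3 = 0.054 per month, or about 5 per 100 patient-months of waiting.
- State separately what exceeding the 2% emergent-surgery figure triggers. Keep that figure and the immediate notification of each such complication.

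Any formal between-arm harm boundary and the layout of the 4-monthly report can stay in the DSMB charter.

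The cost is a short wording amendment. It uses events already collected from randomization, the existing board and the existing report, and needs no extra patients or procedures. The small downside is that the board uses judgement in place of a fixed control-arm limit.
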